9.3.3 Collection and reporting of SAE

All SAEs that occur within 4 weeks after the subjects sign the informed consent form and complete the study, regardless of their cause or drug relevance, must be reported using the SAE

report form. If a serious adverse event (SAE) occurs, the researcher should immediately take appropriate treatment measures for the subjects to ensure their safety. At the same time, the researcher should report to the drug registration applicant, the National Medical Products Administration, the Provincial Food and Drug Administration, the ethics committee of the corresponding clinical trial center, and the Medical Department of the Health Commission and Medical Administration Bureau within 24 hours, and promptly report to the ethics committee of the leading unit. The first report should include the following information as much as possible: source of the report, name of the investigational drug, name of serious adverse event, time of occurrence, severity, duration, relevance to the investigational drug, measures taken, and outcome.

9.3.4 Criteria for determining the severity of AE

Researchers will evaluate the severity based on the five level judgment criteria developed by NCI CTCAE 5.0:

- Level 1, mild; Asymptomatic or with mild signs; For clinical or diagnostic observation only, no medical intervention is required;
- Level 2, moderate; Age appropriate daily life functions are restricted (such as cooking, shopping, making phone calls, etc.);
- Level 3, severe or medically significant but not immediately life-threatening; Causing hospitalization or prolonging hospitalization time; a disability; Restricted daily self-care activities (daily self-care activities refer to bathing, dressing, undressing, eating, toileting, taking medication, etc., but not bedridden);
- Level 4, life-threatening, requiring emergency treatment;
- Level 5, AE related deaths;

9.3.5 Other responsibilities of researchers during follow-up of serious adverse events

Researchers should conduct corresponding examinations and treatments for serious adverse events based on clinical judgment, including necessary clinical laboratory tests, physical examinations, etc. Any inspection results or other updated SAE related information must be followed up with a follow-up report, which has the same time limit and process as the initial report.

10. Test termination/suspension criteria

10.1 The applicant has the right to terminate/suspend this trial. Before terminating/suspending a clinical trial, the applicant must notify the researchers, ethics committee, and the National Food and Drug Administration, and state the reasons. After early termination/suspension of the study, resuming the study must obtain approval from the ethics committee for review;

10.2 Termination/suspension requested by the ethics committee.

11. Regulations for ending clinical trials.

The experiment ends when all participants meet the following conditions:

- 1) All participants in the observational study completed all data collection, and all participants in the continuous monitoring study completed data collection and reporting as required after reaching the study endpoint.
- 2) Or all subjects may die, be lost to follow-up, or withdraw their informed consent.

12. data management

12.1 data management

- 1) Researchers must ensure that the data is true, complete, and accurate;
- 2) When making any corrections to the experimental records, only lines should be drawn and the modified data should be annotated with reasons. The researcher should sign and indicate the date, and the original records should not be erased or covered;
- 3) The laboratory inspection items are complete.

12.2. Data recording and file saving

The subject data on the case report form should be recorded in the form of subject codes, and subjects can only be identified by their subject codes or their initials.

This experiment uses its own APP for data management: from data entry to source data verification requirements, to questioning and answering quality control data, and finally to data locking and export operations. After confirming that there are no doubts about the data, all parties sign the database locking application form, and the data administrator locks the database. After the database is locked, the data administrator exports the analysis database and submits it to the statistical personnel for statistical analysis. The locked data cannot be edited again. Any issues discovered after database locking can be corrected in the statistical analysis program after confirmation.

13. statistical analysis

13.1 Sample size determination

This study is divided into three stages: the first stage is a prospective intervention study, and the second and third stages are observational studies. The sample size of the experiment is mainly based on the requirements of the first stage research, calculated using PASS 15.0 software. Compare the differences in dynamic and static foot posture between the intervention group and the observation group for subjects with foot pain after 4 weeks of intervention. Require bilateral testing, with $\alpha=0.05$, $\beta=0.1$, and a confidence (testing efficiency) of $1-\beta=90\%$. The expected difference in effect between the intervention group and the observation group is 0.8, so each group requires 34 people, for a total of 102 people in the three groups. According to the preliminary epidemiological investigation, the incidence of foot pain events in children is about 12%. The planned recruitment sample size is 1000 people, which can collect about 120 cases of foot pain events, meeting the sample size requirements.

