Expected progress	Starting from January 2024 to December 2024, recruit phase one participants and initiate the study Screening of Phase II subjects and conducting experiments from January 2025 to December 2025

	Screening of Phase III subjects and conducting experiments from January 2026 to December 2027
--	---

List of abbreviations and definitions of terms

abbreviation	definition
WBV	Whole Body Vibration Training: The subject is placed on a vibration platform that provides vertical sinusoidal vibrations to the body, stimulating receptors and causing neuromuscular excitation.
IMU	Inertial Measurement Unit: including gyroscope and accelerometer.

Experimental Procedure Table

project	baseline	Phase I		Phase II	Phase III
		Asymptomatic	Foot pain intervention		
informed consent	✓	✓	✓	✓	✓
Inclusion/exclusion criteria	✓	✓	✓	✓	✓
physical examination	✓	✓	✓	✓	✓
Foot pain VAS score	✓	✓	✓		
All-weather sensors		✓	✓		
WBV Training			✓		
TCM training			✓		
3D foot scan		✓	✓	✓	✓
Foot X-ray in weight-bearing position				✓	
Analysis of Traditional Chinese Medicine Tongue Images				✓	
Body fat measurement				✓	
Saliva gene analysis				✓	
Wrist bone age				✓	
Bone density ultrasound				✓	
Magnetic resonance imaging scan					✓
Gait optical action capture					✓
Surface electromyography collection					✓
Foot pressure test					✓

1. Research background

1.1 research meaning

Foot injury is one of the most common motor system diseases in children, and the most common clinical manifestation is foot pain. At present, there are few reports on the incidence of foot pain in Chinese children. Foreign studies have shown that the incidence of foot pain in children and adolescents is as high as 10% -15%, accompanied by the risk of foot injury and foot deformity. Our preliminary research found the same pattern, with the highest proportion of foot pain among children aged 6-11 in Foshan reaching 12.67%, and the proportion of foot pain gradually increases with age. Among young people who frequently suffer from ankle sprains, about 25% have long-term ankle instability, making ankle injuries a common disease among adolescents and children.

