prevent the occurrence of injuries in advance. It is even more difficult to control the risk of foot injuries and rehabilitation processes in large-scale children. Therefore, we used Huawei HUAWEI S-TAG inertial sensors to observe the foot posture characteristics of children with foot injuries in the early stage. In the study, it was found that the static and dynamic foot posture of children are closely related to foot pain, mainly due to the significant difference in the angle of calcaneus valgus and the swing angle of the longitudinal axis of the foot during gait (toe push off phase) between normal children and children with foot pain. Based on the above, this project focuses on the research of neural network models for key rehabilitation nodes in the core content of foot injury risk prediction, WBV intervention process, and exercise intervention process. Inertial sensors are used to observe foot posture data 24/7, and regular features in gait before injury and during rehabilitation process are mined. Neural network algorithms are used to construct algorithm models, and recognition and evaluation models are established for earlier "compensated", "decompensated", and "key rehabilitation node" gaits before injury. Prompt for decompensated gait before injury occurs, thereby achieving early warning and monitoring of the rehabilitation process before injury occurs. The prediction accuracy of this model approaches the real world infinitely as the amount of training data continues to increase.

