3.2 Secondary endpoint indicators

After the occurrence of foot pain events, a 4-week observation or intervention was conducted under the guidance of researchers, and the evaluation of the improvement of dynamic and static foot posture was ultimately completed.

4. experimental design

4.1 overall design

This clinical study is a prospective intervention study. We plan to recruit 1000 participants aged 6-18. Over the next 4 weeks, sensors were used to collect gait data and record the occurrence of foot pain. Children with foot pain will be enrolled in the observation group, exercise intervention group, or WBV intervention group according to their wishes. After 4 weeks of intervention, analyze and compare the differences in dynamic and static foot posture between the intervention group and the observation group. In the second stage, 120 participants aged 8-10 were selected for an observational study on the correlation between foot development and bone age development, and all levels were completed on the day of the study. In the third stage, 30 participants aged 8-10 years were selected for an observational study of gait dynamics using optical motion capture. Complete all levels of the day.

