4.2 Randomization and blinding

4.2.1 randomization

In the first stage of this study, it is expected that about 12% of the children will experience foot pain, and eligible/ineligible patients will be enrolled according to their willingness to join the observation group, WBV intervention group, or gongfa intervention group, with at least 34 cases in each group, and no randomization will be conducted.

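### Sections 4.2.1 and 13.1 use an undated 12% as the 4-week foot-pain rate and state 34 per group as met, which free choice does not secure; no rule separates children already in pain at screening.

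*Protocol*

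**What the plan says.** Section 13.1 derives 34 children per group (two-sided alpha 0.05, power 90%, expected difference 0.8) and 102 in three groups. It takes a foot-pain incidence of about 12% from a preliminary epidemiological investigation and concludes: "The planned recruitment sample size is 1000 people, which can collect about 120 cases of foot pain events, meeting the sample size requirements".

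Section 4.2.1 applies the same rate to the first stage, where "it is expected that about 12% of the children will experience foot pain". Children then join a group according to their wishes, "with at least 34 cases in each group, and no randomization will be conducted". The period for observing pain is given in section 4.1: "Over the next 4 weeks, sensors were used to collect gait data and record the occurrence of foot pain".

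The background to the 12% is in section 1.1. One figure is from abroad: "the incidence of foot pain in children and adolescents is as high as 10% -15" per cent. The other is the team's own: "the highest proportion of foot pain among children aged 6-11 in Foshan reaching 12.67%, and the proportion of foot pain gradually increases with age".

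A facial VAS for foot pain is taken at screening (section 7.1 and the procedure table). The inclusion and exclusion criteria (sections 5.2 and 5.3) do not mention foot pain. Section 7.2 describes pain events reported through the app during monitoring, confirmation by VAS, and then entry to a group. Section 13.3 compares the gait of children with foot pain and children without symptoms.

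**The concern.** Three things are taken for granted between the 12% and the claim that the requirement is met.

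- **Period and type of the rate.** Neither figure in section 1.1 has a time window. The team's own figure is a highest proportion at ages 6-11, which reads as a prevalence. Neither is described as new pain arising within 4 weeks.
- **Filling of the groups.** The 34 is stated as a minimum, but no quota, cap, extension of recruitment or explicit allowance for loss supports it.
- **Children already in pain.** Apart from researcher judgement, nothing excludes them, and nothing says what follows from a positive screening VAS.

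The third matters most for the main objective, the risk warning model. Section 1.1 states its purpose: "Prompt for decompensated gait before injury occurs, thereby achieving early warning and monitoring of the rehabilitation process before injury occurs". The same section reports a difference in calcaneal valgus and in "the swing angle of the longitudinal axis of the foot during gait (toe push off phase) between normal children and children with foot pain", without saying which comes first, the gait or the pain. If children already in pain are pooled with new cases, a model meant to warn may partly recognise pain that is already there.

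**Working it through.** **1. Reproducing the plan.** Inputs from section 13.1: two-sided alpha 0.05, power 0.90, difference 0.8. No unit or SD is given, and the 34 reproduces when 0.8 is read as a standardised difference. With the noncentral t distribution, df = 2n - 2 and noncentrality 0.8 x sqrt(n/2):

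- n = 33 per group: power 0.893
- n = 34 per group: power 0.902

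So 34 is right, 3 x 34 = 102, and 1000 x 0.12 = 120.

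**2. Break-even rate.** 102/1000 = 10.2% of the children must become cases within the 4 weeks. The margin at 12% is 120 - 102 = 18 cases, or 15%. It has to absorb chance in the total, uneven choice and loss together.

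**3. Chance that every group reaches 34.** Let N be the number of cases among 1000 at rate p, with each case choosing a group independently:

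P(all three >= 34) = sum over N of Binomial(N; 1000, p) x P(all three >= 34 given N, multinomial shares).

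With N fixed at 120 and equal shares the result is 0.70. With N random and equal shares:

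| 4-week rate | Expected cases | P(N >= 102) | P(all three >= 34) | Mean power for 0.8 |
|---|---|---|---|---|
| 8% | 80 | 0.008 | 0.001 | 0.80 |
| 10% | 100 | 0.43 | 0.10 | 0.89 |
| 11% | 110 | 0.80 | 0.33 | 0.91 |
| 12% | 120 | 0.97 | 0.62 | 0.94 |
| 12.67% | 127 | 0.99 | 0.77 | 0.95 |
| 15% | 150 | >0.99 | 0.98 | 0.97 |

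Mean power is the power of a pairwise t-test averaged over the simulated group sizes.

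**4. Sensitivity at 12%.** These inputs are assumptions, because the protocol gives neither preferences nor loss:

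- 40/30/30 preference: P(all three >= 34) = 0.42; mean power 0.91 to 0.94, depending on the pair.
- Equal preference with 10% loss: P(all three >= 34) = 0.27; mean power 0.91.

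**5. Where power gives way.** With equal preference and no loss, mean power drops below 0.90 under a 4-week rate of about 10.5% and below 0.80 under about 8%. With 10% loss the second threshold moves to about 8%/0.9 = 8.9%.

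**6. Children in pain at screening.** This is a reading of the text, not a calculation. Section 7.1 collects the VAS. Sections 5.2 and 5.3 do not use it. Section 7.2 describes entry after a reported event, but then refers to subjects with foot pain as determined by VAS. Sections 4.2.1 and 13.1 count cases without saying whether the pain is new. Section 13.3 sets no limit on when the pain began. No section gives the number of cases with gait recorded before pain.

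**The case against.** - **The 12% has a source.** Section 13.1 names a preliminary investigation, and 12% lies within the 10%-15% of section 1.1. The cohort extends to age 18 and the protocol says pain increases with age, so a figure from ages 6-11 could be too low. This stands: only the period and type of the 12% lack support. A reader might infer that the true 4-week rate is far lower, but the documents neither state nor exclude that.
- **Reaching 34 is not the power criterion.** A group of 33 still gives 0.893 in a balanced comparison, and mean power at 12% stays above 0.90 in every scenario shown. This also stands. A reader might take 0.62 or 0.10 as the chance of an adequate trial. They are only the chance of meeting the protocol's own stated minimum.
- **The sequence runs forward.** Sections 4.1 and 7.2 have children monitored first, with cases following an event reported during monitoring, and section 1.1 already names gait before injury as what is to be mined. A reader might infer that any number of the 120, even all, could lack gait recorded before pain. The text gives no basis for that. The gap is narrower: no rule covers a child with a positive screening VAS.
- **The filter belongs in an analysis plan.** The exact data cut could sit there, and section 13.3 is not described as building the model. But the case count, the claim of adequacy and entry to the groups are fixed in this protocol, and all three depend on how such children are treated.

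**Conclusion.** The point holds as a fault in a sample-size assumption and in the definition of the analysis population. It is not an arithmetic error: 34, 102 and 120 are all computed correctly.

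The minimum group size is stated as met when, at the plan's own 12%, it would be missed in at least one group about 4 times in 10 under equal preference (1 - 0.62 = 0.38). The effect on power is minor if the 4-week rate is 10% or more and becomes serious only below about 8%. These results assume independent choices, equal preference unless stated otherwise, and 0.8 as a standardised difference.

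The more important part is the missing rule for children in pain at screening, because it touches the validity of the warning model. Its size cannot be given, since the documents do not say how many such children to expect. The point should be fixed, but it does not show the trial to be underpowered.

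**What to change.** 1. Restrict the warning model, and any comparison of pain with no symptoms that is used to support it, to children without foot pain on the screening VAS. Use only sensor data recorded before the first pain report.
2. In section 13.1, state the period of the 12% and whether it means new or existing pain. Say whether children with pain at screening count towards the 120. Give expected cases and power over 10%-15%.
3. In sections 4.2.1 and 13.1, restate the 34 per group as a target that depends on choice and loss. Reconcile sections 4.2.1, 7.2 and 13.1 on children with pain at screening.

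The cost is wording in sections 4.2.1, 7.2, 13.1 and 13.3 and a filter on a score already collected, with no extra enrolment. The price is fewer cases in the warning analysis and a less favourable stated count.

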13.2 Definition and selection of analysis set

Use the full analysis set for statistical analysis. Full analysis set (FAS): Includes all enrolled subjects who have received at least one non pharmacological intervention and have measurable baseline foot injury.

13.3 statistical method

Independent sample t-test was used to compare gait parameters between children with foot pain and those without symptoms, while repeated measures ANOVA was used to compare dynamic and static foot posture parameters before and after training intervention.

13.4 Statistical software and general requirements:

- All statistical analyses were conducted using SPSS 25.0 (or higher version).
- Measurement data is described using mean, standard deviation, median, maximum, and minimum values
- Count data is described using frequency and percentage

14. Experimental management

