Inclusion Criteria	Agree to participate in the study, and the legal representative voluntarily signs the informed consent form Children and adolescents aged 6-18 with typical development, regardless of gender

Exclusion criteria	Except for flat feet, there are other congenital deformities of the lower limbs or spine that affect foot posture. In addition to flat feet, there are other muscle, nerve, and bone diseases that affect foot posture. The researchers have determined that they are not suitable to participate in this study
Effectiveness analysis	Main efficacy indicators: Motional foot posture improvement (push off phase foot flip angle) Secondary efficacy indicators: Static foot posture improvement (foot posture index FPI-6)
Security analysis	The detection equipment and methods used in this study mainly include harmless optical motion capture, structured light 3D scanning, wearable sensors, and bioelectrical resistance body composition analysis; X-ray, bone age, ultrasound and other imaging tests are all operated by professional technicians, and the collection environment and methods meet safety requirements; The intervention method is non pharmacological therapy, which is harmless to the human body; The data acquisition and analysis process strictly follows privacy protection regulations, and there is no security risks.
statistical analysis	Analysis set: Use the full analysis set for statistical analysis. Full analysis set (FAS): Includes all enrolled subjects who have received at least one non pharmacological intervention and have measurable baseline foot injury. Sample size determination: According to epidemiological surveys, the incidence of foot pain events in children is about 12%, and it is determined based on similar studies. Statistical analysis: SPSS 25.0 statistical analysis software will be used for statistical analysis
follow-up	Feedback on foot pain events; Execution of martial arts training and vertical rhythm training; The efficacy and adverse reactions of martial arts training and vertical rhythm training.
Statistical methods	The method used is independent sample t-test to analyze gait parameters of normal and poor foot postures, and repeated measures ANOVA to analyze gait and foot posture parameters before and after intervention.

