2.1 Main purpose

Constructing a foot health risk warning model based on wearable sensors

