7.2 Phase One

We plan to recruit 1000 participants aged 6-18 to record their basic health status and static foot posture at baseline. Subsequently, sensors were used to collect gait data for more than 8 hours per day for the next 4 weeks, and all enrolled children wore wearable sensors in their daily lives. The obtained data is uploaded to the cloud server through a mobile application, and remote monitoring and daily event recording are achieved by uploading the data through the APP. When subjects experience foot pain events, they should promptly report to the researchers through the APP. After determining foot pain based on VAS scores, the subjects with foot pain will be enrolled in the observation group, exercise intervention group, and WBV intervention group according to their wishes. Children in the observation group should rest according to medical advice and not participate in sports activities. Children in the intervention group received WBV vertical rhythm or exercise training programs under the guidance of researchers' follow-up. The follow-up time is once a week, and the training lasts for a total of 4 weeks. Using a self-developed app for researchers to remotely monitor and guide children's training movements, and track training progress.

The device uses Huawei S-TAG foot rings, matched with HarmonyOS 2+/Android 6.0+/iOS 9.0+systems; IP68 (GB/T 4208-2017), waterproof rating of 50 meters; Bluetooth: BT 5.0 transmits data; Running Scene

Battery life: Run for 1 hour per day, run 5 days a week, leave it still when not in use, and have a battery life of 30 days.

(1) WBV Vertical Rhythm Training Standard Process: Children enrolled in the study will be trained at home using vertical rhythm equipment under the guidance of researchers and parental supervision. WBV training lasts for 4 weeks, five days a week, with 15 minutes of training per day. Each movement lasts for 30 seconds, and there is a 30 second break between groups.

(2) Standard process for traditional Chinese medicine exercise training: Children enrolled in the group will undergo exercise training under the supervision of their parents, following the teaching of a self-developed APP. The Yi Jin Jing training will last for 4 weeks, five days a week, with 15 minutes of training per day. There will be a total of 12 exercises, each lasting 1 minute, with a 15 second break between groups.

Figure 2 S-TAG Wearable Sensor

7.3 Phase 2

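### The only analysis set requires a received intervention, so the foot-pain versus symptom-free t-test in section 13.3 has no comparator, and the set does not say whether the observation group belongs to it

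*Protocol*

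**What the plan says.** Protocol section 13.2 directs that the full analysis set be used for statistical analysis. It names no other set. Membership has two joint conditions: "Includes all enrolled subjects who have received at least one non pharmacological intervention and have measurable baseline foot injury". The statistical analysis row of the synopsis repeats the rule in the same words.

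Section 13.3 follows directly: "Independent sample t-test was used to compare gait parameters between children with foot pain and those without symptoms". It adds a repeated measures ANOVA of posture parameters before and after the training intervention. The statistical methods row of the synopsis describes the t-test differently: "independent sample t-test to analyze gait parameters of normal and poor foot postures".

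On who receives what:
- Sections 4.1 and 7.2 open the three groups (observation, exercise, WBV) only to children with foot pain.
- The Experimental Procedure Table ticks WBV and TCM training only in the column "Foot pain intervention", not in the asymptomatic column.
- Section 7.2 says of the observation group: "Children in the observation group should rest according to medical advice and not participate in sports activities".
- Section 7.2 also says that in Phase One "all enrolled children wore wearable sensors in their daily lives".

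Section 13.1 sizes the trial on the difference between intervention and observation groups in children with foot pain: 34 per group, 102 in all.

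**The concern.** An analysis set has to contain the children whom the stated analyses compare. Here the only set is defined by receipt of an intervention, while the first analysis in 13.3 needs a group that by design receives none. An analyst who applies 13.2 as written cannot run that test. An analyst who runs it must depart from the protocol and choose the population without guidance.

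The second problem is an omission within the same rule. The set is the one in which intervention would be compared with observation, yet the rule does not say whether a child advised to rest has received a non-drug intervention. Children choose their group and the study is unblinded (4.2.1, 4.2.2), so membership of the control group should be fixed in the text before data are seen.

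**Working it through.** **1. The plan's own figure.** Section 13.1 gives two-sided alpha 0.05, power 90% and an expected difference of 0.8. No SD or unit is stated, so I read 0.8 as a standardised difference (assumption).
- Normal approximation: n = 2 × (1.960 + 1.282)² / 0.8² = 32.8, so 33 per group.
- Exact two-sample t-test: 33.83, so 34 per group, with power 90.2% at 34.
- 3 × 34 = 102, and 1000 × 0.12 = 120 expected foot-pain cases.

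The stated 34, 102 and 120 all reproduce. The present point does not change them; it concerns who is counted afterwards.

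**2. Symptom-free children against the 13.2 rule.**
- Condition one is a received intervention. Group entry needs foot pain (4.1, 7.2) and training is ticked only for foot-pain children (procedure table), so symptom-free children fail it.
- Condition two is measurable baseline foot injury. Section 5.1 gives criteria for foot pain and foot posture but no measure of injury. The argument does not need this condition, because both must hold and the first already fails.
- Symptom-free children in the set: 0, whatever the incidence.
- Number affected at 12%: 1000 × (1 − 0.12) = 880. At the 10% to 15% cited in section 1.1: 900 to 850. These counts assume that the incidence applies to the 4-week monitoring window and that all 1000 are monitored.
- The intended 13.3 contrast is therefore about 120 versus 880. Under 13.2 its symptom-free arm is 0.

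**3. The observation group against the same rule.** The texts point both ways.
- Towards exclusion: sections 3.2, 4.1, 7.2 and 13.1 set observation against intervention as alternatives, and 7.2 gives training only to the intervention groups.
- Towards inclusion: the procedure table has a single column for foot-pain children, labelled "Foot pain intervention"; section 8 describes children with foot-pain events, without distinction, as being trained; and advised rest is itself a directed regimen.

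| Reading | Planned children in the set | Control arm in the 13.1 comparison |
|---|---|---|
| Rest is not an intervention | 102 − 34 = 68 | 0 of 34 |
| Rest is an intervention | 102 | 34 of 34 |

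The 34 is the planned minimum per group (4.2.1), and children choose their group, so actual numbers may differ. If the 120 expected cases split equally (assumption), the set holds 80 or 120.

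**4. The two t-test wordings.** The synopsis contrasts normal with poor foot posture; 13.3 contrasts pain with no symptoms. These are different groupings. The synopsis version could be run within the set, because children with foot pain may have neutral or pronated feet on the section 8.2 scale. The empty arm belongs to the 13.3 version only.

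**The case against.** The best defence is that the set was plainly meant for the intervention comparison. Section 13.3 names its own two populations, so any analyst would see that the rule cannot apply to the t-test. The result would be a visible impossibility, not a hidden bias, and a statistical analysis plan, which is not at hand, could settle it. The intention is probably as described, and I agree that no concealed bias follows. But neither 13.2 nor the synopsis limits the set in that way. The protocol is not silent: it prescribes one set and states the rule twice. A later plan that used symptom-free children would contradict it.

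Three stronger readings are tempting, and the documents do not support them.
- **That the observation group is excluded.** This is one reading. The 34-versus-0 result is its worst case, and section 13.1 would be unworkable under it, which suggests that it was not intended. The documents support only that membership is unstated.
- **That the warning model is left without event-free children.** The main purpose is "Constructing a foot health risk warning model based on wearable sensors", and such a model needs event-free children. Section 13 never mentions the model or applies the set to it, and section 7.2 collects sensor data from every enrolled child.
- **That the differing t-test wordings are part of the analysis-set fault.** They are a separate, minor inconsistency.

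**Conclusion.** As written, section 13.2 empties one arm of an analysis stated in section 13.3. That part is definite: the comparator's share of the set is zero at any incidence. The count of about 880 of 1000 rests on 12% holding over the 4-week window with no dropout.

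The observation group's position is an ambiguity, not a proven loss. Between 0 and 34 of the 102 planned children (0 to 33%) are at issue, depending on whether advised rest counts as an intervention. It still needs settling, because the trial is sized on the comparison with that group.

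The before/after comparison in trained children can be run as planned, and the sample size is unaffected. This should be fixed: the contradiction is clear and the correction is cheap.

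**What to change.** Amend section 13.2 and the matching synopsis row.

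(a) State that the 13.3 t-test of foot-pain versus symptom-free children uses all enrolled Phase I children with sensor gait data, whatever their pain or intervention status.

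(b) Define the full analysis set for the intervention comparison as all children with VAS-confirmed foot pain who entered any of the three groups, naming the observation group explicitly. This replaces both present conditions, the received intervention and the baseline foot injury. Take the pre-intervention posture value from data already collected: static posture at baseline (7.2) and sensor gait data from before the group period. Do not make a new measurement at group entry a condition. The protocol describes no FPI-6 assessment at that point, so such a condition could add a visit procedure or exclude children.

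(c) Minor: reconcile the synopsis t-test wording with 13.3, or list the two contrasts as separate comparisons.

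The set in (a) would also suit the warning model. If the sponsor wants that, a sentence can say so, since section 13 assigns the model no population at present.

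Cost: one paragraph in 13.2, the same text in the synopsis and one sentence to align the t-test wording. No further participants, visits or measurements are needed.
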